7.2 Subject Withdrawal from the Study

The subject may withdraw or may be withdrawn from the study:

- If they decide to do so, at any time and irrespective of the reason
- At the specific request of the Sponsor

Subject discontinuation from IMP or withdrawal from the study should be avoided as much as possible. Every attempt should be made to restart IMP if medically appropriate and approved by Medical Monitor, irrespective of the duration of holding IMP.

In the event of withdrawn from the study during the treatment period, if possible, an early discontinuation visit (procedures same as Visit 9) needs to be performed as soon as possible and an on-site follow-up visit (procedures same as Visit 10) after 12 weeks from the last dose should be conducted. If the subject is unwilling to attend the on-site follow-up visit, a follow-up phone call should be attempted if the subject agrees, to collect safety information (monitoring AE, pregnancy status, concomitant medications) (refer to Section 1.3).

In the event of withdrawn from the study during the follow-up period, if possible, an on-site follow-up visit (procedures same as Visit 10) is recommended to complete as soon as possible followed by a phone call follow-up at 12 weeks from the last dose to collect safety information (monitoring AE, pregnancy status, concomitant medications). If the subject is unwilling to attend an on-site

Version 6.0 46 of 138 April 11, 2024

follow-up visit, a phone call follow-up at 12 weeks from the last dose should be attempted if the subject agrees (refer to Section 1.3).

If the subject withdraws informed consent for disclosure of future information, the Sponsor may retain and continue to use any data collected before such a withdrawal of consent.

Note: For subjects discontinued from IMP or withdrawn from study, no additional PK and ADA sampling except EOT and EOS visits (if possible) is required after IMP discontinuation.

Handling of subjects with suspected COVID-19 infection:

If a subject develops fever or symptoms suspected of being a result of COVID-19 during the study, they will be instructed to follow-up with their regular healthcare provider or follow the instructions for suspected COVID-19 cases per their local health authority.

A subject may be withdrawn by the Investigator based on discussion with the Sponsor and Medical Monitor under the following circumstance:

• any confirmed COVID-19 case that warrants withdrawal in the judgment of the Investigator or Sponsor to protect the safety of the subject, other study subjects or study site staff.

7.3 Study Pauses for Safety Reasons

In order to monitor and protect the safety of study subjects, to ensure early insight into any safety signal, and for early elimination of any potential safety hazard for an individual subject or a full cohort/entire study population, the Medical Monitor will review all AEs from the entries in the eCRF on an ongoing basis and SAE reports as received. An independent DMC will be established and will review all study data pertaining to subjects' safety on a regular basis to adjudicate the overall safety of the subjects in this study. In addition, the DMC will be notified, and a meeting may be called for each case of IMP discontinuation due to an IMP related safety reason.

Study will be paused pending prompt review by DMC if 2 or more subjects experience similar SAE or severe AE assessed as related to IMP, or discontinue IMP for safety reasons assessed as related to IMP.

Study will be paused if any of the following assessed as related to IMP occurs, pending prompt review of the case(s) by the DMC: death, suicide attempt, serious changes in behavior (such as

Version 6.0 47 of 138 April 11, 2024

psychosis or the development of impulse control disorders or addictive behavior), cardiac arrhythmia or AEs pertaining to the pituitary gland.

7.4 Loss of Subjects to Follow-Up

A subject will be considered lost to follow-up if she repeatedly fails to return for scheduled visits and is unable to be contacted by the study site.

The following actions must be taken if a subject fails to return to the clinic for a required study visit:

- The site must attempt to contact the subject and reschedule the missed visit as soon as possible (and within the visit window, where one is defined) and counsel the subject on the importance of maintaining the assigned visit schedule and ascertain whether or not the subject wishes to and/or should continue in the study.
- In cases in which the subject is deemed lost to follow-up, the Investigator or designee must
 make every effort to regain contact with the subject (where possible, three telephone calls
 and, if necessary, a certified letter to the subject's last known mailing address or local
 equivalent methods). These contact attempts should be documented in the subject's medical
 record.

Should the subject continue to be unreachable, she will be considered to have withdrawn from the study.

8 Study Assessments and Procedures

Study procedures and their timing are summarized in the SoA (Table 1-1). Protocol waivers or exemptions are not allowed.

Adherence to the study design requirements, including those specified in the SoA, is essential and required for study conduct.

All screening evaluations must be completed and reviewed to confirm that potential subjects meet all eligibility criteria. The Investigator will maintain a screening and enrollment log to record details of all subjects screened and to confirm eligibility or record reasons for screening failure, as applicable.

Procedures conducted as part of the subject's routine clinical management (e.g., mammography) and obtained before signing of the informed consent form (ICF) may be utilized for Screening

Version 6.0 48 of 138 April 11, 2024

purposes provided the procedures met the protocol-specified criteria and were performed within the time frame defined in the SoA.

Repeat or unscheduled samples may be taken for safety reasons or for technical issues with the samples.

Informed Consent

Informed consent must be documented according to Section 10.1.3.

Eligibility Criteria

All inclusion and exclusion criteria will be reviewed by the Investigator or designee to ensure that the subject qualifies for the study.

Subject Identification Card

All subjects will be given a subject identification card identifying them as subjects in a research study. The card will contain study site contact information (including direct telephone numbers) to be used in the event of an emergency. The Investigator or qualified designee will provide the subject with a subject identification card immediately after the subject provides written informed consent. At the time of randomization, site personnel will add the randomization number to the subject identification card.

The subject identification card also contains contact information for the emergency unblinding call center so that a healthcare provider can obtain information about IMP in emergency situations where the Investigator is not available.

Demographic information

The following demographic information will be recorded:

- Age
- Ethnic origin
- Race
- Height in cm
- Body weight (in kg)

Medical history

Version 6.0 49 of 138 April 11, 2024

A medical history will be obtained by the Investigator or qualified designee. The medical history will collect all active conditions and any condition diagnosed prior to signing informed consent that the Investigator considers to be clinically significant. Details regarding the disease for which the subject has enrolled in this study will be recorded separately and not listed as medical history.

Prior and concomitant medications review

The Investigator or qualified designee will review prior medication use and record prior medications taken by the subject within 1 month prior to Screening. For medications related to the inclusion/exclusion criteria with specific washout period, refer to Section 10.5 for the time requirement.

The Investigator or qualified designee will record medication, if any, taken by the subject during the study through the last visit. Concomitant medications will be recorded until last study visit.

All reasonable measures will be taken to decrease potential transmission of COVID-19; for example, study staff and physicians will wear surgical masks and gloves and/or face shields while meeting with subjects and will wash their hands per the Center for Disease Control (CDC)/World Health Organization (WHO)/regional health authority guidelines before, between, and after meeting each subject.

8.1 Efficacy Assessments

8.1.1 Electronic-Diary (e-Diary)

All subjects will be administered an e-Diary after adequate training at Visit 2. Subjects are required to record uterine bleeding and endometriosis-associated pain every day at around the same time for the entire duration of the study. The use of rescue medications for endometriosis-associated pain will also be recorded. Compliance to e-Diary filling will be assessed as shown in the SoA (refer to Section 1.3). Subjects need to return the e-diary devices after the completion of study participation or after withdrawal from the study.

8.1.2 Evaluation of the need for Rescue Medication

Subjects will be supplied rescue pain medication (as listed in Table 6-3) that should be used only for endometriosis-associated pain throughout the study duration. Assessment will be based on the average number of rescue medication consumed by the subject and the percentage of days the subject took rescue medication.

Version 6.0 50 of 138 April 11, 2024

8.1.3 Numeric Rating Scale (NRS) for Pain

NRS pain scale will be used to measure DYS from Baseline to Week 12 and Baseline to Week 24 with Pain Scale ranging from 0 (no pain) to 10 (severe pain). Subjects will assess in the e-Diary their endometriosis-associated pain during the past 24 hours (last calendar day). NMPP and DYSP will be also measured using the NRS pain scale from Baseline to Week 12, and Week 24.

Refer to Section 10.6 for the template.

8.1.4 Endometriosis Daily Impact Pain Scale

Endometriosis Daily Impact Pain Scale will be used to record the mean change every month from Baseline to Week 12 and 24 with the Pain scale ranging from 0 (no pain) to 3 (severe pain).

Based on the subject's response to the question "Did you have your period in the last 24 hours (last calendar day)?" in the daily e-Diary, the subject will be asked to assess either their dysmenorrhea or non-menstrual pelvic pain as follows:

Dysmenorrhea (DYS)

Subjects will be asked to assess their DYS and its impact on their daily activities. Subjects will be prompted to "Choose the item that best describes your pain during the last 24 hours (last calendar day) when you had your period."

0	None	No discomfort
1	Mild	Mild discomfort but I was easily able to do the things I usually do
2	Moderate	Moderate discomfort or pain. I had some difficulty doing the things I usually do
3	Severe	Severe pain. I had great difficulty doing the things I usually do

Non-Menstrual Pelvic Pain (NMPP)

Subjects will be asked to assess their NMPP and its impact on their daily activities. Subjects will be prompted to "Choose the item that best describes your pain during the last 24 hours (last calendar day) without your period."

0	None	No discomfort	

Version 6.0 51 of 138 April 11, 2024

1	Mild	Mild discomfort but I was easily able to do the things I usually do
2	Moderate	Moderate discomfort or pain. I had some difficulty doing the things I usually do
3	Severe	Severe pain. I had great difficulty doing the things I usually do

Dyspareunia (DYSP)

Subjects will be asked to assess their dyspareunia (described as 'pain during sexual intercourse'). Subjects will be prompted to "Choose the item that best describes your pain during sexual intercourse during the last 24 hours (last calendar day)."

	Not applicable	I was not sexually active for reasons other than my endometriosis or did not have sexually intercourse
0	None	No discomfort during sexual intercourse
1	Mild	I was able to tolerate the discomfort during sexual intercourse
2	Moderate	Intercourse was interrupted due to pain
3	Severe	I avoided sexual intercourse because of pain

8.1.5 Uterine Bleeding

Subjects will be prompted to indicate if they had "Did you have any uterine bleeding in the last 24 hours (last calendar day)?" Subject will then document the intensity of the bleeding as follows:

0	None	
1	Spotting	A light amount of bleeding noted, no protection or panty shield only
2	Light	1 to 2 regular tampons or pads required in 24 hours
3	Medium	3 to 4 regular tampons or pads required in 24 hours
4	Heavy	More than 4 tampons or pads required in 24 hours

Version 6.0 52 of 138 April 11, 2024

8.2 Safety Assessments

Planned time points for all safety assessments are provided in the SoA.

8.2.1 Physical Examinations

A complete physical examination will include, at a minimum, assessments of General appearance, HEENT (head, eyes, ears, nose, throat), Neck (including thyroid), Lung/pulmonary, Chest (including breast), Cardiovascular, Abdomen, Back, Neurological, Extremities, Skin and Lymph nodes, and will be performed at Visit 1, Visit 9 and Visit 10. Height (cm) and weight (kg) will also be measured and recorded at specified period shown in the SoA (refer to Section 1.3).

A brief physical examination will include, at a minimum, assessments of General appearance, HEENT (including extra-ocular movements), Neck, Lung/pulmonary, Breast, Cardiovascular, Abdomen, Extremities and Skin, and will be performed at Visit 2, Visit 3, Visit 4, Visit 5, Visit 6, Visit 7, and Visit 8. Additional physical examination may be necessary based upon the subjects' complaints.

Investigators should pay special attention to clinical signs related to previous serious illnesses.

8.2.2 Vital Signs

Vital signs will be assessed from Screening Period to EOT period and during the follow-up visit. Tympanic body temperature, pulse rate, respiratory rate, and blood pressure will be assessed. Blood pressure and pulse measurements will be assessed with a completely automated device. Manual techniques will be used only if an automated device is not available.

Blood pressure and pulse measurements should be preceded by at least 5 minutes of rest (e.g. in a sitting position) for the subject in a quiet setting without distractions (e.g., television, cell phones).

8.2.3 Pelvic examination

The pelvic examination should specifically document presence or absence of uterine or adnexal induration and/or tenderness, with description of tenderness (location, intensity, e.g., mild, moderate or severe) if present. The results of pelvic examination will be used for CPSSS.

8.2.4 Electrocardiograms

12-lead ECG will be obtained as outlined in the SoA using an ECG machine that automatically calculates the heart rate and measures PR, QRS and QT. QT interval will be corrected for heart rate using Fridericia's correction formula (QTcF) and Bazett's correction formula (QTcB) respectively.

Version 6.0 53 of 138 April 11, 2024

8.2.5 Clinical Safety Laboratory Assessments

Refer to Section 10.2 for the list of clinical laboratory tests to be performed and to the SoA for the timing and frequency. Blood draw will not exceed 500 mL during the entire study period.

The Investigator must review the laboratory report, document this review, and record any clinically significant abnormal changes occurring during the study in the AE section of the eCRF. The laboratory reports must be filed with the source documents. Clinically significant abnormal laboratory findings are those which are not associated with the underlying disease, unless judged by the Investigator to be more severe than expected for the subject's condition.

All laboratory tests with values considered clinically significant abnormal during participation in the study or within 14 days after the last dose of IMP should be repeated until the values return to normal or Baseline, or are no longer considered clinically significant by the Investigator or Medical Monitor, or subject lost to follow-up or death.

- If such values do not return to normal/Baseline within a period of time judged reasonable by the Investigator, the etiology should be identified, where possible, and the Sponsor notified.
- All protocol-required laboratory assessments, as defined in Section 10.2, must be conducted in accordance with the laboratory manual and the SoA.
- If laboratory values from laboratory assessments not specified in the protocol and performed at the institution's local laboratory result in the need for a change in subject management or are considered clinically significant by the Investigator (e.g., are considered to be an SAE or an AE or require dose discontinuation), then the results must be recorded in source document.

8.2.6 Transvaginal Ultrasound (TVU) Assessments

Assessments for TVU include, but are not limited to, the following:

- Endometrial thickness (double layer, mm)
- Other endometrial findings such as heterogeneity or other abnormality
- Presence, size and appearance of ovarian cysts or masses
- Presence, location and size of uterine fibroids
- Endometriomas

The Screening TVU may be repeated per protocol (e.g., ovarian cyst criteria) or as clinically appropriate. An unscheduled (elective) TVU may also be performed as clinically indicated for subject evaluation during the course of the study.

8.2.7 Dual Energy X-ray Absorptiometry (DXA)

DXA results of the lumbar spine, total hip, and femoral neck will be obtained at screening period and Visit 9. A central bone density vendor will be used to conduct blinded reads of DXA scans and manages the longitudinal quality control of DXA scanners at each imaging center. The data from these analyses will be electronically transferred from imaging center to the study database. Subject treatment management will be made based on the central review.

For individual subject, the degree of bone loss that requires a follow-up DXA scan(s) as follows:

- a) Obtain a 6-month post-treatment follow-up DXA scan for subjects with change from pretreatment baseline of \leq -2.0% in the lumbar spine or \leq 2.5% total hip, or Z-score \leq -2.0 (i.e., below the expected range for age) at any anatomic site (lumbar spine, total hip, or femoral neck).
- b) If the subject does not meet the criteria for adequate recovery on her DXA scan at post-treatment month 6, refer to a bone specialist (Define adequate recovery as change from pre-treatment baseline of > -1.5% at the lumbar spine and > -2.0% at the total hip).
- c) Refer to a bone specialist those subjects with Z-score \leq -2.0 at any anatomic site at post-treatment month 6 (or on their final DXA scan if they do not follow-up as instructed).

The window period for EOT visit and post-treatment month 6 DXA scan is ± 14 days.

Subjects who prematurely discontinue IMP treatment prior to week 11 will not have a DXA at the EOT visit or in the Post-treatment Follow-up Period. Subjects who become pregnant during the study will not have protocol required DXA scans.

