6.2 Preparation, Handling, Storage, and Accountability	Added "Requirements for aseptic operation should be followed during IMP preparation." "the reconstituted solution should be stored between 2°C and 8°C" is revised to "the reconstituted solution should be stored at 2- 8°C or room temperature". Deleted "If the solution has been stored above 25°C, it must no longer be used for application and should therefore be discarded.	According to updated <investigational administration="" and="" clinical="" for="" hmi-115em201="" instruction="" preparation="" products="" trial="">, Revision 01</investigational>
8 Study Assessments and Procedures	Deleted Table 2 in "Study procedures and their timing are summarized in the SoA (Table 1-1 and Table 1-2)."	Keep consistency with the removal of Part 2 study.
8.1 Efficacy Assessments (for Part 1 and Part 2)	Deleted "(for Part 1 and Part 2)" in the subtitile of this part	Keep consistency with the removal of Part 2 study.
8.2.7 Dual Energy X-ray	b) If the subject does not meet the criteria for adequate recovery on her	Post treatment DXA may not reflect the effect of HMI-115 on

Absorptiometry (DXA)	DXA scan at post-treatment month 6, refer to a bone specialist perform another DXA scan at post-treatment month 12 (Define adequate recovery as change from pre-treatment baseline of > -1.5% at the lumbar spine and > -2.0% at the total hip). c) Refer to a bone specialist those subjects with change from pre-treatment baseline in BMD of ≤ 3.0% at the lumbar spine and/or total hip, and/or Z-score ≤ -2.0 at any anatomic site at post-treatment month 12 6 (or on their final DXA scan if they do not follow-up as instructed). The window period for EOT visit and, post-treatment month 6 and month 12 DXA scan is ±14 days.	BMD, especially after 12 months, because after a subject leaves the study, she will not be prohibited from medications that influence her BMD.
8.3.1 Patient Global Impression of Change (PGIC) Score	Subjects will score the PGIC as shown in the SoA (refer to Table 1-1, and Table 1-2).	Keep consistency with the removal of Part 2 study.
9.1 Statistical Hypotheses	Added "One interim analysis is planned. More details of the interim analysis are presented in Section 9.5."	Introduce the interim analysis.

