8.2.6 Transvagina 1 Ultrasound (TVU) Assessments	Change from "Significant ovarian findings on TVU include complex ovarian cyst > 3 cm or simple ovarian cyst > 5 cm. For the purposes of this study, an ovarian cyst whose appearance is consistent with an endometrioma will be considered to be complex" to "The Screening TVU may be repeated per protocol (e.g., ovarian cyst criteria) or as clinically appropriate. An unscheduled (elective) TVU may also be performed as clinically indicated for subject evaluation during the course of the study".	Modified according to update in eligibility criteria section
8.2.7 Dual energy X-ray absorptiometry (DXA)	Adjusted monitoring criteria and procedure for DXA Added "Subjects who prematurely discontinue treatment prior to week 11 will not have a DXA at the EOT visit or in the Post-treatment Follow-up Period"	Adopt the suggestions from the U.S. FDA HMI-115 is unlikely to induce bone loss from its MOA and previous studies data. Treatment less than 3 months is very short and unlikely to detect any changes through DXA.

8.11 CPSSS	Delete "from a 28 day recall period"	To make it more flexible to cover longer menses cycle (for instance 35 days)
9.3.1 Variables for Stratification of Randomization	This study employs a stratified randomization with region (China, United States) being the only two stratification factors: 1) region 2) participation in the intensive PK sampling subset (Yes, No). These stratification factors will be taken into account in the statistical analyses.	Add stratum of intensive PK to ensure subject in this subset will be well distributed by treatment arm.
9.4.3 Primary Efficacy Endpoints	Added "The time frame for a visit for which the rescue medication use will be attributed to is defined as 5 weeks (35 calendar days) preceding the visit."	To clarify the timeframe of rescue medication information to be collected for analysis
9.4.7.7 DXA scan	Change "bone marrow density" to "bone mineral density"	Corrected a typo
10.1.5 Committees Structure	Changed DMC members to "two unblinded experts in the fields of gynecology and one independent unblind biostatistician". Details see DMC charter. Remove "The DMC meeting will also include an unblinded Sponsor clinician and an unblinded Sponsor statistician. Unblinded Sponsor representatives will be independent of the study, and study personnel will remain blinded".	To make committee member as odd for voting and easy to make conclusion

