1. INTRODUCTION

HMI-115 is a highly specific human monoclonal antibody that will be investigated for safety and efficacy in pre-menopausal women with moderate to severe endometriosis associated pain.

A First in-human (FiH) study with HMI-115 has already established the safety and tolerability of HMI-115 when administered subcutaneously in post-menopausal women aged between 45 to 65 years in single doses up to 240 mg and multiple doses up to 90 mg once every 2 weeks (Q2W) for 6 weeks. This study aims to evaluate the safety and efficacy of HMI-115 versus a placebo in pre-menopausal women aged 18 to 49 years diagnosed with moderate to severe endometriosis associated pain.

The analyses described in this Statistical Analysis Plan (SAP) are based upon the following study documents:

- Study Protocol Version 6.1 (19 Sep 2024)
- Electronic Case Report Form (eCRF), Version 6.0 (12 Dec 2023)

Data will be summarized and listed according to the SAP. The details will be reflected in the document of Table, Listing, and Figure Shells.

The planned analyses identified in this SAP may be included in clinical study reports (CSRs), regulatory submissions, or future manuscripts. Also, post hoc exploratory analyses not necessarily identified in this SAP may be performed to further examine study data. Any post hoc, or unplanned, exploratory analyses performed will be clearly identified as such in the final CSR.

In addition, the SAP V1.3_special version for research paper publication is generated for the requirement of research paper publication only. Compared to the SAP V1.3, the change is that the SAF will be same as the PAS for all safety analysis.

PROJECT OVERVIEW

[figure not shown]

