8.4.5 DXA Scan

Bone mineral density data from DXA scan will be summarized descriptively for each treatment group at each visit. The within-group %CFB will be summarized and will be compared with a paired t-test by visit; the between-group difference for each visit will be compared with an ANOVA, and two-sided 95% CI for the differences between each of the treatment groups and the placebo group will be presented. Data from post treatment Month 6/Month 12 (before Protocol version 5.0) will not be analyzed for clinical study report (CSR).

In addition, DXA scan will be summarized for each treatment group by category the %CFB as $\geq -3\%$, $-3\% \text{ to } -5\%$, $-5\% \text{ to } -8\%$ and $<-8\%$.

A by-subject listing of DXA scan data will be provided.

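### Protocol 8.2.7 item a) prints the total-hip trigger for the 6-month follow-up DXA as ≤ 2.5%, without the minus sign that the other five limits carry

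*Protocol*

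**What the plan says.** Protocol 8.2.7 opens its three items as defining, for the individual subject, "the degree of bone loss that requires a follow-up DXA scan(s) as follows".

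- Item a) calls for a scan six months after treatment if any one of three limits is met. The lumbar spine limit is ≤ -2.0% and the Z-score limit is ≤ -2.0. Between them stands the hip limit, printed after a ≤ sign as "2.5% total hip, or Z-score".
- Item b) sends subjects without adequate recovery at month 6 to a bone specialist. It defines recovery as "change from pre-treatment baseline of > -1.5% at the lumbar spine and > -2.0% at the total hip".
- Item c) refers subjects with a Z-score ≤ -2.0 at month 6.

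Note 13 to the Schedule of Activities and the bone entry in the risk table (Protocol 2.3.1) both send the reader to 8.2.7, so this section is the operative rule. The SAP does not restate the trigger. SAP 8.4.5 says "DXA scan will be summarized for each treatment group by category the %CFB as" and then lists categories cut at -3%, -5% and -8%, so a loss is a negative number. The same SAP section keeps the post-treatment Month 6 and Month 12 scans out of the CSR analysis.

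**The concern.** A limit of ≤ 2.5% on a scale where loss is negative does not describe bone loss. It takes in no change and gains of up to 2.5%. It also lies above the level at which item b) treats the hip as recovered, so a subject could be recalled on the hip criterion while her hip already meets the recovery definition.

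The practical stake is site conduct. Protocol 10.1.11 requires the protocol to be followed exactly, and Section 8 rules out waivers. A site applying the printed text would recall subjects with no hip loss for a scan that falls after the 12-week follow-up period. A site that inferred -2.5% would, on paper, be deviating. Two sites could therefore apply different rules to the same result.

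**Working it through.** The plan contains no calculation behind this limit, so there is nothing to reproduce. The check sets the printed limits side by side and compares them.

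**Inputs, all from Protocol 8.2.7**

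| Item | Measure | Limit as printed | Minus sign |
|---|---|---|---|
| a | Lumbar spine, % change | ≤ -2.0% | yes |
| a | Total hip, % change | ≤ 2.5% | **no** |
| a | Z-score, any site | ≤ -2.0 | yes |
| b | Lumbar spine, recovery | > -1.5% | yes |
| b | Total hip, recovery | > -2.0% | yes |
| c | Z-score, any site | ≤ -2.0 | yes |

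Six limits, five with a minus sign.

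**Gap between trigger and recovery limit** (recovery limit minus trigger, same site)

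- Spine: -1.5 - (-2.0) = 0.5 points.
- Hip with a minus sign: -2.0 - (-2.5) = 0.5 points.
- Hip as printed: -2.0 - 2.5 = -4.5 points.

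With the minus sign the hip rule has the same 0.5-point structure as the spine rule. Without it the order is reversed.

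**Who is caught only because the sign is missing**

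- Hip changes above -2.5% up to +2.5%: width 2.5 - (-2.5) = 5.0 points.
- The part of that band already above the hip recovery limit, from above -2.0% up to +2.5%: width 2.5 - (-2.0) = 4.5 points.
- Spot checks: changes of -3.0% and -2.5% are flagged under both limits; -2.4%, 0% and +2.5% only as printed; +2.6% under neither.

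Every change that a -2.5% trigger would flag is also flagged by the printed one, so the error runs in one direction only.

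**Illustration, not relied on.** The documents give no mean or SD for hip BMD change. Assume a normal distribution with SD 1% to 3%, and take the share flagged by the hip limit alone as Φ((limit - mean)/SD).

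| Assumed mean | As printed (≤ 2.5%) | With minus sign (≤ -2.5%) |
|---|---|---|
| 0% | 99.4% (SD 1) to 79.8% (SD 3) | 0.6% (SD 1) to 20.2% (SD 3) |
| -1% | 99.98% (SD 1) to 87.8% (SD 3) | 6.7% (SD 1) to 30.9% (SD 3) |

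These shares should not be multiplied by the 152 planned subjects. Under 8.2.7, subjects who stop IMP before week 11 or become pregnant do not have the end-of-treatment scan.

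**The case against.** The strongest objection is that the sign may be on the printed page and have been lost when the PDF was converted to text. There is some support for this. Item a) has the unhyphenated form of pre-treatment while item b) has the hyphen, which could mark a character dropped at a line end. Superseded wording of the same section in the Revision History (version 4.0 to 5.0) also shows an unsigned limit, "in BMD of ≤ 3.0% at the lumbar spine and/or total hip", next to signed ones. The possibility stands, and it is why the first step is to look at the page. The line-end explanation is weak for this limit, however. If a line broke inside that word, the hip limit would fall about 55 characters into the next line, and the signs on either side of it in the same sentence survived. The superseded 3.0% is not counted as an error, and it fits an author's omission as well as a conversion loss.

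Second, the SAP is written to Protocol 6.1 of 19 September 2024, and only 6.0 was available. This also stands: the limit may already have been corrected.

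Third, item a) is an either/or rule. A subject flagged on Z-score alone may already satisfy both percentage limits in b), so being flagged while meeting the recovery limits is not in itself contradictory. That is true of the Z-score, which is a different measure. It does not explain a hip trigger set above the recovery limit for the same hip measurement.

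Fourth, a sensible reader would take 2.5% as a loss, and subject management follows central reading. This is fair, and it is why the point ranks low. It does not make the printed threshold right.

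**Conclusion.** The point holds on the text of Protocol 6.0. The total-hip trigger is printed without a minus sign, and -2.5% is almost certainly what was meant. The stated purpose of the section, the five signed limits around it and the 0.5-point spacing at the spine all support that value.

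Its importance is minor. The printed rule widens the hip trigger by 5.0 percentage points but misses nobody with a hip loss of 2.5% or more. Specialist referral under b) and c) rests on limits with their signs intact. No efficacy analysis is affected, and the month-6 scans are outside the CSR analysis. The cost of the error is unnecessary recalls and inconsistent practice between sites; how many recalls cannot be estimated from the documents.

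Confidence is medium. The conclusion assumes that the sign is absent on the printed page and that Protocol 6.1 did not correct it.

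**What to change.** 1. Check the sign in the source PDF of Protocol 6.0 and in Protocol 6.1. If it is there, nothing more is needed.
2. If it is absent, change the total-hip trigger in 8.2.7 item a) to ≤ -2.5%. The Revision History for version 1.0 to 2.0 records "Adjusted monitoring criteria and procedure for DXA" and gives FDA suggestions as the reason, so that correspondence may confirm the intended value. The documents do not show that it names a hip limit.
3. If follow-up is already complete, leave the protocol as it is and state in the CSR which hip limit was applied in deciding who was recalled.

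The cost is one character, by administrative letter or with the next amendment, or one sentence in the CSR.
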